9.6. Drug Accountability

In accordance with ICH requirements, the investigator will, at all times, be able to account for all IMP furnished to the study site. A drug accountability record will be maintained for this purpose. The investigator must maintain accurate records indicating dates and quantity of IMP received, to whom it was dispensed (subject-by-subject accounting) and accounts of any IMP accidentally or deliberately destroyed. All unused IMP not involved in immediate subject dosing will be maintained under locked, temperature-controlled storage at the study site.

9.7. Compliance Monitoring

Prior to beginning the administration of IMP, subjects and/or their caregiver will be trained on dosing administration and must exhibit proper technique. Subjects and/or their caregiver will be trained on the completion of the study diary and will complete a study diary entries to record all IMP administration and will bring it, along with all IMP kits including used vials to each visit. Each time IMP is dispensed compliance will be encouraged. Subject diary training is an ongoing process as the diary will be reviewed with the subject at each visit to monitor compliance with IMP administration.

10. SAFETY ASSESSMENTS AND PROCEDURES

The following safety assessments will be evaluated: AEs, physical examinations, clinical laboratory test results (chemistry, hematology, HbA1c, ██████████, and urinalysis, ██████████ hepatitis serology, IGRA for TB test) and vital signs. All safety assessments will be performed at times outlined in the Schedule of Study Events ([Table 1](#)). Additional (unscheduled) safety assessments may be performed as needed.

10.1. Adverse Events

AEs will be collected from signing of the ICF and followed by the investigator until the AE is resolved or stabilized. AEs occurring prior to the administration of IMP will only be reported if they are related to study procedures. Any and all safety measures (which includes standard of care activities) should be provided by the study site to the subject. Any study site follow-up should be documented.

Refer to [Section 13.4](#) for additional details on the handling of AEs and SAEs.

10.2. Medical and Surgical History

Medical and surgical history will be obtained at the Screening Visit/Visit 1. Medical history will include a review of the following systems: general, dermatological, respiratory, cardiovascular, gastrointestinal, genitourinary, gynecological, endocrine, musculoskeletal, hematological, neuropsychological, immune (allergies), and head, eyes, ears, nose, and throat. Historical and current medical conditions including date of last menstrual period for female subjects will be recorded.

10.3. Current Medical Conditions

At each visit after screening, subjects will be asked about any changes in medical conditions, specifically new medical conditions and worsening of existing medical conditions. Any changes since the Screening Visit/Visit 1 will be recorded as AEs, as appropriate.

10.4. Physical Examinations

A complete physical examination will be performed at the Screening Visit/Visit 1 and the End of Study/Early Termination Visit. The complete physical examination includes evaluation of the head, eyes, ears, nose, throat, neck (including thyroid), cardiovascular system (including assessment of heart, peripheral pulses, presence or absence of edema), lungs, abdomen (including liver and spleen, bowel sounds), lymph nodes, musculoskeletal system (including spine, joints, muscles) neurological system (including cranial nerves, reflexes, sensation, strength), skin, extremities and other conditions of note.

A limited physical examination, including evaluation of lungs, heart, abdomen, extremities and assessment for edema will be done at all other visits.

The findings of the physical examinations will be recorded. Any change from the Screening Visit/Visit 1 physical examination that is considered clinically significant by the investigator will be recorded as an AE.

10.5. Vital Signs

Vital signs will be obtained after the subject has been seated for 5 minutes (minimum) and will include systolic and diastolic blood pressures, pulse rate, respiratory rate, and body temperature. Additionally, at the Screening Visit/Visit 1 and the Baseline Visit/Visit 2, blood pressure will be measured at least 3 times, with 5 minutes between assessments after the subject has been seated for a minimum of 5 minutes prior to the initial blood pressure assessment.

The investigator may perform additional unscheduled vital sign measurements to evaluate or manage a suspected AE. These unscheduled vital sign measurements should be obtained after the subject has been seated for at least 5 minutes, if possible. Unscheduled vital signs will be recorded.

At a minimum, the date of vital signs at the Screening Visit/Visit 1 will be recorded. The date and time for all other vital signs will be recorded.

Screening/Baseline

A subject with systolic blood pressure > 150 mm Hg and diastolic blood pressure > 90 mm Hg (average of 3 assessments) at the Screening Visit/Visit 1 or Baseline Visit/Visit 2 does not qualify for the study.

On Study Assessments

If an on-study vital sign is not in the reference range, an AE will be recorded if the investigator determines the change is clinically significant or requires a change in the subject's clinical management.

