	
• [REDACTED]■ [REDACTED]■ [REDACTED]■ [REDACTED]■ [REDACTED]■ [REDACTED]■ [REDACTED]■ [REDACTED]■ [REDACTED]■ [REDACTED]■ [REDACTED]■ [REDACTED]
Entry Criteria: Male or nonpregnant, nonlactating female subjects 18 years of age or older with primary FSGS (confirmed by renal biopsy) who are nephrotic (uPCR > 3.0 mg/mg and estimated glomerular filtration rate [eGFR] at least 30 mL/min/1.73 m ²) and who have failed to achieve sustained CR or PR of proteinuria with at least 1 prior immunosuppressive therapy OR intolerance at least 1 prior immunosuppressive therapy will be enrolled in the study. Subjects must be treated with an angiotensin converting enzyme inhibitor or angiotensin receptor blocker (or have documentation of intolerance), for at least 4 weeks prior to Screening Visit/Visit 1 with blood pressure no more than 150/90. Subjects also must be negative for hepatitis B, hepatitis C, have no history of tuberculosis (TB) or other contraindication as per the United States (US) Prescribing Information for Acthar, have no history of Type 1 or Type 2 diabetes mellitus, or have any clinically significant infection. Subjects cannot have taken Rituximab or cyclophosphamide 24 weeks prior to Screening Visit/Visit 1, any investigational treatments for FSGS or oral corticosteroids (unless used to treat FSGS) for 12 weeks prior to Screening Visit/Visit 1, any intravenous/intramuscular corticosteroids (unless used to treat FSGS) for 8 weeks prior to Screening Visit/Visit 1, or have been involved in a therapeutic drug/device trial (other than for FSGS) 4 weeks prior to Screening Visit/Visit 1.	
Concomitant Medications and Treatments: A stable dose of angiotensin-converting enzyme inhibitor/ angiotensin receptor blocker is required throughout study participation. Subjects requiring other antihypertensive medications must be on a stable dose at least 4 weeks prior to the first dose of Acthar. Subjects are not permitted to take any enteral or parenteral corticosteroid, live or live-attenuated vaccine or systemic immunosuppressive medication during the study. All medications and nondrug therapies (eg, blood transfusions, oxygen supplementation) at Screening Visit/Visit 1 and throughout the study will be recorded.	

Study Title: Treatment of Proteinuria Due to Treatment Resistant or Treatment Intolerant Idiopathic Focal Segmental Glomerulosclerosis: A Prospective Study of Acthar (PODOCYTE)	

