10. Must have a mean systolic blood pressure \leq 150 mm Hg and a diastolic blood pressure of \leq 90 mm Hg determined by the average of \geq 3 seated readings taken at least 5 minutes apart at Screening Visit/Visit 1 and at the Baseline Visit/Visit 2.
11. Must be able to communicate effectively with study personnel.
12. Must be able and willing to follow all protocol requirements and study restrictions.
13. Must be able and willing to return for all study visits.

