^a If subject is not currently receiving immunosuppressant treatment for FSGS at the Screening Visit/Visit 1, the Baseline Visit/Visit 2 will occur >2 days and < 63 days after the Screening Visit/Visit 1. ^b Corticosteroids used for the treatment of FSGS (see exclusion Criterion 14 for corticosteroid use to treat other conditions).	

21. Has current or recent (within 6 months of the Screening Visit/Visit 1) drug or alcohol abuse as defined in Diagnostic and Statistical Manual of Mental Disorders, Fifth Edition, Diagnostic Criteria for Drug and Alcohol Abuse ([American Psychiatric Association, 2013](#)).
22. Has any of the following laboratory abnormalities at the Screening Visit/Visit 1:
- Hemoglobin \leq 8.0 g/dL.
 - Platelets \leq 50,000 cells/ μ L.
 - Absolute neutrophil count (ANC) \leq 1,000 cells/ μ L.
 - Aspartate aminotransferase (AST), alanine aminotransferase (ALT), or total bilirubin $>$ 2 times the upper limit of normal (ULN).
 - Glycosylated hemoglobin (HbA1c) $>$ 6.5%.
 - Positive Hepatitis B surface antigen (HBsAg) or Hepatitis B core antibody (HBcAb).
 - Positive Hepatitis C virus antibody (HCV) and HCV polymerase chain reaction (PCR) \geq 25 IU/mL (HCV PCR will be automatically analyzed if HCV is positive).
 - Positive or indeterminate interferon gamma release assay (IGRA).
23. Has any other clinically significant disease, disorder or laboratory abnormality (including those listed on the Prescribing Information Section 5: Warnings and Precautions [[Mallinckrodt ARD LLC, 2015](#)]) which, in the opinion of the investigator (by its nature or by being inadequately controlled), might put the patient at risk due to participation in the study, or may influence the results of the study or the subject's ability to complete the study.

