10.6. Height and Weight

Height will be collected at screening only. Weight will be collected at specified times during the study.

10.7. Clinical Laboratory Tests, HbA1c, Serum Cystatin C, Serum Electrolytes, IGRA, Urinalysis, and Pregnancy Tests

The clinical laboratory tests are listed in [Section 24.1](#). All clinical laboratory tests will be done at a central laboratory facility except urine pregnancy (at the site) and IGRA (local laboratory). Specific instructions for collection, storage and shipment of clinical laboratory samples will be provided in a separate laboratory manual.

Samples for laboratory testing at all visits may be collected under fasted or nonfasted conditions. The date and time of the sample collection must be documented on the laboratory report. Investigators must review and sign laboratory reports. The clinical significance of each laboratory abnormality will be documented. New clinically significant laboratory abnormalities or clinically significant changes in laboratory values will be reported as AEs, as appropriate.

Hematology with differential, serum chemistry, other specific tests, and urinalysis samples will be collected at the specific times starting at screening and throughout the study.

In addition:

- All female subjects of child-bearing potential will have a serum pregnancy test at the Screening Visit/Visit 1, and a urine pregnancy test at the Baseline Visit/Visit 2 and at specified visits throughout the study. Results must be available prior to dosing with protocol mandated IMP. Subjects with positive results will be ineligible for study entry (Screening Visit/Visit 1) or withdrawn from the study. Any female subject that becomes pregnant during the study will be immediately withdrawn and the pregnancy report as per [Section 13.5](#).

If applicable, the subject's agreement to use contraception throughout their study participation, and for 4 weeks after ending study participation, will be documented.

- HBsAg and HBcAb will be performed at the Screening Visit/Visit 1. Results of these tests must be negative or nonreactive for subjects to qualify for the study.
- HCV will be performed at the Screening Visit/Visit 1. A positive HCV will automatically trigger a HCV PCR analysis. HCV PCR must be < 25 IU/mL to qualify for the study.

[REDACTED]

[REDACTED]

[REDACTED]

[REDACTED]

[REDACTED]

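### Section 10.5 disqualifies only when both blood pressures are over their limits, whereas Inclusion 10 fails a subject when either one is

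*Combined protocol and SAP*

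**What the plan says.** Blood pressure eligibility is stated in three places in the protocol.

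- **Section 6.1, Inclusion 10.** It begins "Must have a mean systolic blood pressure" and sets a limit of at most 150 mm Hg for systolic and at most 90 mm Hg for diastolic. Both are taken from the average of no fewer than "3 seated readings taken at least 5 minutes apart", at Visit 1 and again at Visit 2.
- **Section 1.1, Synopsis, Entry Criteria.** Subjects enter "with blood pressure no more than 150/90".
- **Section 10.5, Screening/Baseline paragraph.** The subject declared ineligible, at Visit 1 or Visit 2, is "A subject with systolic blood pressure > 150 mm Hg and diastolic blood pressure > 90 mm Hg (average of 3 assessments".

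The first paragraph of Section 10.5 also says that at these two visits "blood pressure will be measured at least 3 times, with 5 minutes between assessments".

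**The concern.** Section 10.5 tells sites how to take the qualifying readings and places an eligibility sentence beside that instruction, with no cross-reference to Section 6.1. A site that screens from that sentence would not be told to exclude a subject with only one pressure over its limit, although Inclusion 10 excludes that subject.

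The connective cannot safely be dismissed as loose idiom. In Sections 9.3.1 and 9.3.2 the protocol defines accelerated hypertension by systolic of at least 180 and diastolic of at least 100, with the word *and* emphasised. A reader has reason to take *and* between two pressures literally.

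What is at stake is consistent screening. Section 3.5 lists hypertension among the known potential risks of the drug, and changes in vital signs are a primary endpoint (Section 4.1). With about 60 subjects at about 100 sites (Section 5.4), the average is 60/100 = 0.6 subjects per site, so most sites would have little experience with which to settle a conflict in the text.

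**Working it through.** No sample size or power figure is involved, so the check is one of logic.

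**Inputs.** Let S be mean systolic and D mean diastolic pressure, in mm Hg.

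- Inclusion 10 is met when S ≤ 150 and D ≤ 90.
- The Section 10.5 sentence disqualifies when S > 150 and D > 90.

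**Step 1: what failing Inclusion 10 means.** The negation of (S ≤ 150 and D ≤ 90) is (S > 150 **or** D > 90).

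**Step 2: compare with Section 10.5.** Both inequalities have been reversed but *and* has been kept. The connective for the visits was switched: Inclusion 10 must hold at Visit 1 *and* Visit 2, and Section 10.5 disqualifies at Visit 1 *or* Visit 2, which is the correct negation. Only the connective between the two pressures was not switched.

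**Step 3: the gap.** Subjects who fail Inclusion 10 but are not caught by Section 10.5 are those with exactly one of S > 150 and D > 90 true.

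| Reading | Inclusion 10 | Section 10.5 sentence | Consistent? |
|---|---|---|---|
| 140/80 | met | not disqualified | yes |
| 150/90 | met | not disqualified | yes |
| 160/95 | failed | disqualified | yes |
| 151/90 | failed | not disqualified | no |
| 150/91 | failed | not disqualified | no |
| 170/85 | failed | not disqualified | no |
| 145/100 | failed | not disqualified | no |

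A check of every whole-number pair with systolic from 90 to 200 and diastolic from 50 to 120 gave the same result. The gap is exactly the pairs with one, and only one, pressure over its limit. No pair meets Inclusion 10 and is also disqualified by Section 10.5, so the sentence never turns away a subject whom Inclusion 10 accepts.

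**Step 4: if the two texts matched.** Had the Section 10.5 sentence been the exact negation of Inclusion 10, the gap would be empty. That shows only what consistency requires, not which rule is clinically right.

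**Step 5: number of readings.** Inclusion 10 and the first paragraph of Section 10.5 both allow more than three readings, but the disqualifying sentence refers to an average of 3. If a site takes four, the text does not settle which readings enter the average.

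**The case against.** The strongest reply is that nothing in the Section 10.5 sentence is false. It gives a sufficient condition for failing: everyone it turns away also fails Inclusion 10, and it never says that the rest qualify. Inclusion 10 remains in force. Section 6.1 requires all inclusion criteria at both visits, Table 1 schedules an eligibility review at both, Section 8.2 repeats the requirement, and Section 9.1 enrols only subjects who meet every criterion and has baseline failures reported as screen failures. Exclusion 10 also bars current uncontrolled hypertension, although the term is not defined there, so it is only a partial backstop.

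This stands, and it limits the point. A reader might infer that Section 10.5 sets a second, looser entry rule under which a subject at 170/85 may be enrolled. The documents do not support that: such a subject is ineligible when the protocol is read as a whole.

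It is also fair to say that harm depends on a site applying Section 10.5 without returning to Section 6.1. No passage tells sites to do so, and nothing in the documents shows that it has happened. The synopsis wording is shorthand, so the comparison rests mainly on Inclusion 10.

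The reply does not remove the discrepancy. Two operative passages state a decision threshold for the same measurement at the same visits, and they differ for a definable group of subjects. Nothing in Section 10.5 signals that its statement is partial.

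**Conclusion.** The discrepancy is real and minor. The Section 10.5 sentence is narrower than the negation of Inclusion 10, and the difference is exactly the subjects with one pressure over its limit. This follows from the wording alone and needs no distributional assumption. The consequence, a risk of inconsistent screening and eligibility deviations, assumes that some sites use the Section 10.5 sentence at the point of measurement.

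No frequency is claimed, because the documents give no blood pressure distribution. A reader might also infer damage to the primary safety analysis. The documents do not support that: Sections 12.2 and 12.7 include every enrolled subject who receives at least one dose, so the Safety Population is the same whether or not a subject breached Inclusion 10.

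**What to change.** Reconcile the synopsis, Inclusion 10 and Section 10.5 so that one blood pressure eligibility rule is stated once, and replace the Section 10.5 sentence with a cross-reference to it. In the same edit, use one wording for the number of readings averaged. The sponsor decides the rule; this point takes no position on it.

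Optionally, check existing Visit 1 and Visit 2 readings for subjects with exactly one pressure over its limit, and record any found as potential eligibility deviations.

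The cost is a one-sentence protocol correction with the matching edits and, if wanted, a query on data already collected. It needs no additional patients, visits or procedures.

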10.6. Height and Weight

Height will be collected at screening only. Weight will be collected at specified times during the study.

10.7. Clinical Laboratory Tests, HbA1c, Serum Cystatin C, Serum Electrolytes, IGRA, Urinalysis, and Pregnancy Tests

The clinical laboratory tests are listed in [Section 24.1](#). All clinical laboratory tests will be done at a central laboratory facility except urine pregnancy (at the site) and IGRA (local laboratory). Specific instructions for collection, storage and shipment of clinical laboratory samples will be provided in a separate laboratory manual.

Samples for laboratory testing at all visits may be collected under fasted or nonfasted conditions. The date and time of the sample collection must be documented on the laboratory report. Investigators must review and sign laboratory reports. The clinical significance of each laboratory abnormality will be documented. New clinically significant laboratory abnormalities or clinically significant changes in laboratory values will be reported as AEs, as appropriate.

Hematology with differential, serum chemistry, other specific tests, and urinalysis samples will be collected at the specific times starting at screening and throughout the study.

In addition:

- All female subjects of child-bearing potential will have a serum pregnancy test at the Screening Visit/Visit 1, and a urine pregnancy test at the Baseline Visit/Visit 2 and at specified visits throughout the study. Results must be available prior to dosing with protocol mandated IMP. Subjects with positive results will be ineligible for study entry (Screening Visit/Visit 1) or withdrawn from the study. Any female subject that becomes pregnant during the study will be immediately withdrawn and the pregnancy report as per [Section 13.5](#).

If applicable, the subject's agreement to use contraception throughout their study participation, and for 4 weeks after ending study participation, will be documented.

- HBsAg and HBcAb will be performed at the Screening Visit/Visit 1. Results of these tests must be negative or nonreactive for subjects to qualify for the study.
- HCV will be performed at the Screening Visit/Visit 1. A positive HCV will automatically trigger a HCV PCR analysis. HCV PCR must be < 25 IU/mL to qualify for the study.

[REDACTED]

[REDACTED]

[REDACTED]

[REDACTED]

[REDACTED]

12. STATISTICAL METHODS AND PLANNED ANALYSIS

12.1. General Considerations

Data will be listed, analyzed, and included in the clinical study report. Data will be analyzed as described in the statistical analysis plan. Descriptive statistics for continuous variables will include number of values, mean, SD, median, minimum, and maximum, unless otherwise noted. Frequency and percentages will be calculated for categorical variables. All statistical significance testing will be 2-tailed using $\alpha = 0.05$, unless otherwise specified. Data summary and analyses will be performed with SAS 9.2 or higher.

12.2. Analysis Populations

- The Intent to Treat (ITT) Population will include all enrolled subjects who receive 1 or more doses of IMP and who contribute any exploratory data to the study.
- The Per Protocol Population will include the subset of the ITT population who complete the study as per protocol. Completer populations will be further defined in the statistical analysis plan.
- The Safety Population will include all enrolled subjects who receive 1 or more doses of IMP.

12.3. Efficacy Assessments

12.3.1. Primary Efficacy Endpoint

There is no primary efficacy endpoint.

12.3.2. Secondary Efficacy Endpoints

There are no secondary efficacy endpoints.

12.4. Primary Safety Endpoints

The primary safety endpoints to be evaluated include a summary of the general safety profile including AEs (serious and non-serious), physical examinations, clinical laboratory tests, vital signs, medical and surgical history, height and weight.

12.5. Exploratory Endpoints

Exploratory endpoints will examine [REDACTED]

[REDACTED]
[REDACTED]
[REDACTED]

[REDACTED] [REDACTED]

[REDACTED]	[REDACTED]
[REDACTED]	[REDACTED]
[REDACTED]	[REDACTED] [REDACTED]
[REDACTED]	[REDACTED] [REDACTED]
[REDACTED]	[REDACTED] [REDACTED] [REDACTED] [REDACTED]
[REDACTED]	[REDACTED] [REDACTED]

[REDACTED]	[REDACTED]
[REDACTED]	

Exploratory endpoints include:

- [REDACTED]
- [REDACTED]
- [REDACTED]
- [REDACTED]
- [REDACTED]
- [REDACTED]
- [REDACTED]
- [REDACTED]
- [REDACTED]
- [REDACTED]
- [REDACTED]
- [REDACTED]
- [REDACTED]
- [REDACTED]
- [REDACTED]

